1.2 Study Device Details

The table below demonstrates many aspects of the devices under study.

	AQUACEL® Ag+ Extra™	Cutimed® Sorbact®
Mode of Action	The mode of action of these wound dressings is by absorption and fluid retention. When in contact with wound exudate, the dressing forms a cohesive gel; this gelled material enables intimate contact of the dressing with the wound bed.	Cutimed® Sorbact® binds microorganisms, such as Staphylococcus aureus (including MRSA), Streptococcus species, Escherichia coli , Pseudomonas aeruginosa and Candida albicans , as shown in-vitro. These microorganisms are removed from the wound each time the dressing is changed.

	AQUACEL® Ag+ Extra™	Cutimed® Sorbact®
	
The dressings demonstrate antimicrobial activity through the presence of silver, an antimicrobial agent.
 
The addition of EDTA and benzethonium chloride enables the dressing to disrupt wound biofilm and sessile attached bacteria in contact with the dressing
	
Duration of Use	AQUACEL® Ag+ Extra™ can be worn for up to 7 days, dressings should be changed earlier if clinically indicated. On partial thickness (second degree) burns, dressings may remain in place for up to 14 days. The need for AQUACEL® Ag+ Extra™ should be re-assessed after 14 days and alternative wound management considered where appropriate	Cutimed® Sorbact® can be left in place for up to 7 days, should the clinical condition allow
Intended Use	AQUACEL® Ag+ Extra™ Dressings have been designed to be used as a primary dressing. They are intended to be used under the direction of a healthcare professional for wounds, which are at risk of infection or show signs of infection, or where biofilm is suspected to be present, and in accordance with the indications for use.	Cutimed® Sorbact® is indicated for use in management of clean, contaminated, colonised, or infected wounds with moderate to high levels of exudate, such as surgical wounds, traumatic wounds, pressure ulcers, diabetic ulcers, and leg ulcers.
Storage Conditions	According to manufacturer's packaging	According to manufacturer's packaging

1.3 Device Regulatory Classification

The study devices used in this study are approved in Europe and are classified according to MDR in the table below.

	AQUACEL® Ag+ Extra™	Cutimed® Sorbact®
MDR Classification	Class III	Class IIb

2 Risks and Benefits of the Devices used in this Study

The section below details the risks and benefits of the devices used in this study.

2.1 Risks of the Devices

The risks associated with using the study device(s) in the study are no different than in standard of care, as they will be used according to their intended use statements. Please refer to IFU Sections PRECAUTIONS and OBSERVATIONS for any information regarding adverse events and any steps that should be taken to avoid them, as well as information about other warnings and precautions in relation to the device.

Anticipated Adverse Device Effects

The anticipated adverse device effects are known reactions to the study devices. The list of known anticipated adverse device effects include, but are not limited to: allergic reaction, bleeding, pain/discomfort in area of wound, skin irritation around wound, and infection.

2.2 Residual Risks

The study devices used on this study are applied according to indications for use. By participating in this study, it is anticipated that the residual risks are the same as not participating in the study. The device manufacturers have performed qualification testing on the device and device components and appropriate quality control measures have been implemented into production.

2.3 Risk of Interactions with Concomitant Medical Treatments

No interactions with concomitant medications are noted in the IFU for either study device.

2.4 Mitigation of Risk

Additional action to mitigate risks are not anticipated, as the devices are used in a way that is standard of care.

2.5 Benefits of the Device

There are no additional benefits of using this device in the study than in standard of care.

2.6 Risk to Benefit Rationale

Considering the information listed in this section, it can be concluded that there are no additional risks to individuals exposed to devices in the study compared to in standard of care. There are no risks of physical harm associated with participation in this study, as this is a study evaluating a commercially approved wound dressing when used as intended, with follow up procedures performed per standard of care. No treatment is added or removed due to a patient's participation in the study. The device IFUs contain additional information related to the anticipated risks associated with the use of the dressings and wound care.

2.7 Other Medical Devices to be Used in the Study

Any additional dressings or complimentary therapies such as compression, off-loading devices, and similar used in this study will be applied as in intended use and availability in the market while following their respective IFUs.

3 DESIGN OF CLINICAL INVESTIGATION

3.1 Study Design

The study is a post market, multi-centre, randomised, open label, global prospective study to compare the performance of AQUACEL® Ag+ Extra™ and Cutimed® Sorbact® dressing in the management of patients with venous leg ulcers (VLUs).

The VLUs will be treated with AQUACEL® Ag+ Extra™ (Experimental Arm) or Cutimed® Sorbact® (Control Arm) for up to 4 weeks. The WLUs will then be managed the with Standard of Care for up to 10 weeks, or until the wound has healed or the dressing is no longer clinically indicated. Crossover of dressings is not permitted.

3.2 Justification and Scientific Rationale for Design

This study compares the performance of AQUACEL® Ag+ Extra™ verses Cutimed® Sorbact® in patients with VLUs. Literature supports the use of silver dressings in these types of wounds, as this may promote healing. This study is designed to collect this type of data on Convatec's AQUACEL® Ag+ Extra™.

3.3 Minimisation of Bias

Bias in studies can impact results in any study. To minimise bias, the following steps, which include, but are not limited to, have been taken:

- Multiple sites and geographies have been selected, which reduces the instrumentation and performance biases.
- Randomization minimizes confounding bias.

4 OBJECTIVES OF THE CLINICAL STUDY

4.1 Primary Objective(s)

The primary objective of the study is to compare the effectiveness of AQUACEL® Ag+ Extra™ verses Cutimed® Sorbact® in the management of patients with venous leg ulcers (VLUs).

4.2 Endpoints

4.2.1 Primary Endpoint

- Complete wound closure as defined by 100% epithelialisation of the wound surface (Gould 2019).

4.2.2 Secondary Endpoints

- Percent change in study wound area at 4 weeks (primary treatment period).
- Satisfactory clinical progress defined as 40% reduction in study wound area at 4 weeks (primary treatment period)
- Percent change in target wound area at 12 weeks.

4.2.3 Exploratory Endpoints

- Time to complete wound closure.
- Wound characteristics:
 - Eschar tissue presence and percentage
 - Slogh/Fibring tissue presence and percentage
 - Healthy granulation tissue presence and percentage
 - Unhealthy granulation tissue presence and percentage
 - Epithelial tissue presence and percentage
 - Exudate volume category (low, medium, high)
 - Exudate type
 - Odour
 - Condition of the wound edge
 - Condition of the peri-wound skin
 - Presence of erythema
 - Signs of infection
- Wound-QOL-14.
- Pain on a Numeric Rating Scale from 0 to 10 where 0 is no pain at all and 10 is the worst imaginable pain.
- Wound treatment type after the study mandated treatment.

4.2.4 Safety endpoints

Safety will be characterized by a summary of the incidence of adverse events (AEs), device-related AEs, and serious device-related AEs.

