5 POPULATION AND DURATION OF THE STUDY

It is proposed that the study is conducted in Poland, Germany, and Colombia. Additional sites in additional countries may be recruited. The study sample will be recruited from the Investigators available clinical population.

Individual subject duration of participation in the study is up to 12 weeks. It is anticipated enrolment will take 12 months and the overall study duration is anticipated to be approximately 18 months.

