8.3 Completed Subject

Subject has completed the study if the subject has completed the final study visit (84 days follow-up visit) or earlier if all study wounds have healed prior to 84-day follow-up visit. If subject has multiple wounds, the subject exits the study when the last study wound heals or when subject attends the final study visit, whichever occurs first. Study completion can occur between the scheduled study visits.

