10.2 Visit 2: Day 14 (+/- 2 days)

The following procedures and data are collected at this visit. All information on this visit is required. Crossover to the non-randomized study dressing is not permitted.

- Review of concomitant medications, documenting any changes (medication used, route, dose, unit, frequency, indication, start date, stop date or ongoing)
- Wound assessment
 - Wound size (measured in cm at the longest point and across the widest point, as well as depth)
 - Wound bed appearance
 - Exudate level, colour and consistency
 - Condition of peri-wound skin
 - Maximum pain level on a scale of 0 to 10 within the last 24 hours

- Level of odour on a scale of 0 to 10 for the study participants and mild/medium/strong for the clinician.
- Therapeutic Index for Local Infections (TILI) score
- Number of days, since last visit, where compression was not applied (including documentation of reason for no compression)

A clinician decision is required at this visit regarding continuation of the randomised dressing (AQUACEL® AG+ Extra™ or Cutimed® Sorbact®) or transition to long-term management per standard of care. In subject with multiple study wounds the decision is made for each study wound separately. For example, one wound can be selected for Option 1 and another wound for option 3.

Option 1: An additional 14 days of treatment with randomised dressing (AQUACEL™ Ag+ Extra™ or Cutimed® Sorbact®) is required.

Option 2: Further treatment with randomised dressing is not indicated. The wound should be further managed per standard of care.

Option 3: Clinician determines that a non-standard of care treatment is needed. Treatment with the randomised dressing is discontinued.

Regardless of the option chosen, the subject remains in the study and is followed-up until the study exit (see section 8.2)

Once the decision has been made on the treatment option, the following information will be collected.

- Dressing application according to clinician decision (randomised dressing or other dressing) (name, size and lot number is recorded)
- Documentation of any additional products used
- Document any additional therapies
- Document and address any Adverse Events
- Document and address any Serious Adverse Events
- Number of intermediate visits where dressings were changed between scheduled visits (this is the number of times a subject received a new dressing since the last visit)
- Wound-QOL-14 (only if Option 2 or 3 has been selected).

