10.6 End of Study Visit (Study Exit)

The study exit visit will occur when:

- the subject exits the study for any reason, including that all study wounds have healed; or
- The subject attends Visit 7.

Completion of end of study or appropriate forms is required.

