11.2 Adverse Events Categories and Relationship Determination

All AEs (regardless of relationship to the study procedures or severity) occurring from enrolment up to and including the subject's final study visit will be recorded by the Investigator. AEs may be either spontaneously reported to Investigator or elicited during questioning and examination of a subject. All identified AEs must be recorded in the patient record and on the Adverse Event case report form. If known, the diagnosis of the underlying illness or disorder should be recorded, rather than its individual symptoms.

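### Safety is defined only as AE incidence, although AE recording ends at healing and dressing duration is at open-label discretion, so crude percentages may not be comparable if either differs by arm

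*Combined protocol and SAP*

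**What the plan says.** The whole safety endpoint in the protocol (4.2.4, repeated in the synopsis) is: "Safety will be characterized by a summary of the incidence of adverse events (AEs), device-related AEs, and serious device-related AEs". Section 18.7 defines the Safety Population as subjects randomised and treated, with no time element. Section 18 plans no safety test and no safety margin, and leaves analysis detail to an SAP whose text is not in the supplied document.

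Three other parts of the protocol decide how long each subject contributes.

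- **Recording window (11.2).** AEs "occurring from enrolment up to and including the subject's final study visit will be recorded by the Investigator".
- **End of follow-up (8.3, 10.6).** With several wounds, "the subject exits the study when the last study wound heals or when subject attends the final study visit, whichever occurs first". The exit visit takes place when "the subject exits the study for any reason, including that all study wounds have healed". Section 5 sets the ceiling: "Individual subject duration of participation in the study is up to 12 weeks". No safety contact after healing is described.
- **Dressing exposure (10.2, 10.3, Table 9.3-1).** The trial is a "randomised, open label, global prospective study". At Day 14, "A clinician decision is required at this visit regarding continuation of the randomised dressing", wound by wound. One choice is "Option 2: Further treatment with randomised dressing is not indicated. The wound should be further managed per standard of care". Section 10.3 and a footnote to Table 9.3-1 leave use after Day 28 to the investigator as well. Whatever is chosen, the subject stays in follow-up.

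**The concern.** A subject whose wounds close in week 3 can contribute three weeks of AE recording; one whose wound stays open contributes twelve. Both count as one in the denominator of an incidence. If one arm heals faster, it is watched for less time and will show fewer subjects with an AE at the same underlying rate. A truly higher AE rate in that arm could be masked in the same way.

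The plan allows for such a difference. It tests superiority after non-inferiority (18.2) and lists time to closure as an exploratory endpoint (4.2.3). Two arms with equal closure at Day 84 can still differ in how early they close.

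Device-related AEs have a second dependence. The anticipated effects in 2.1 are largely local to the wound, so their number should follow time on the dressing. That time is set by someone who knows the arm.

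**Working it through.** **Source of the healing inputs.** The protocol gives no AE rate and no sample size for safety. Its stated total of 206 (18.4) concerns healing and reproduces: with 80% closure in both arms, a 15-point margin, one-sided 0.05 and 85% power, n per arm = (1.645 + 1.036)² × 2 × 0.8 × 0.2 / 0.15² = 102.2, so 103 per arm and 206 in total. From this I take 80% closure as the reference and a 15-point gap as a wide scenario.

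**Assumptions (not in the documents).** One wound per subject, no dropout, exit at healing or week 12, and the same constant AE rate μ in both arms. I use μ = 0.05 per week and vary it.

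**Follow-up, constant healing hazard.** λ = −ln(1 − p)/12; mean follow-up = p/λ.

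- p = 0.80: λ = 0.1341, mean 5.96 weeks
- p = 0.75: λ = 0.1155, mean 6.49 weeks
- p = 0.65: λ = 0.0875, mean 7.43 weeks

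For 80% v 65% the ratio is 7.43/5.96 = 1.25.

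**Follow-up, healing spread evenly over 12 weeks.** Mean = 12(1 − p/2), which is 7.2 v 8.1 weeks for 80% v 65%, a ratio of 1.13.

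**Crude incidence of at least one AE.** With constant hazards it is μ/(μ + λ) × [1 − e^(−12(μ + λ))]. With even healing it is 1 − [(1 − p)e^(−12μ) + p(1 − e^(−12μ))/(12μ)].

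| Scenario, μ = 0.05 | Faster arm | Slower arm | Gap |
|---|---|---|---|
| 80% v 80%, either model | same | same | 0 |
| 80% v 75%, constant hazard | 24.2% | 26.1% | 1.9 points |
| 80% v 65%, even healing | 28.9% | 31.9% | 3.0 points |
| 80% v 65%, constant hazard | 24.2% | 29.4% | 5.2 points |

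In the last row the gap is 2.5 points at μ = 0.02 and 7.6 at μ = 0.10. The true rate ratio is 1.00 throughout.

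**Does the remedy remove it?** Under constant hazards, mean time to first AE or exit is [1 − e^(−12(μ + λ))]/(μ + λ). Dividing crude incidence by this returns μ = 0.05 in both arms. For a Day 28 window, crude incidence is still 14.2% v 15.4% (the constant-hazard formula with 4 in place of 12), because λ also implies 1 − e^(−4λ) = 42% v 30% healed by week 4. Censoring at exit gives 1 − e^(−4 × 0.05) = 18.1% in both arms.

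**Dressing exposure to Day 28.** Let q be the share continuing among those still open at Day 14, and f(t) = (1 − e^(−λt))/λ. Mean days are 7 × [f(2) + q(f(4) − f(2))]. With 80% closure in both arms, f(2) = 1.754 and f(4) = 3.096. An assumed q of 50% v 70% gives 17.0 v 18.9 days, 11% more. Equal q gives equal exposure.

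**The case against.** The case against is substantial.

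- **No comparison is planned.** Section 4.2.4 promises a summary, without a test or margin, and does not define incidence. This stands. Side-by-side percentages in a randomised trial will nonetheless be read as a comparison.
- **The SAP may say more.** This also stands. The point is limited to what the protocol states and what the SAP should therefore contain.
- **The bias is conditional.** The design uses a single 80% figure and hypothesises similar effectiveness. A reader might infer that the arms will be observed for unequal times; the documents do not support that. They show that observation depends on healing, not that healing will differ.
- **The size depends on chosen inputs.** A 15-point gap puts the truth at the non-inferiority boundary. With 103 per arm, the standard error of the 5.2-point difference is √[(0.242 × 0.758 + 0.294 × 0.706)/103] = 6.2 points, so the artefact is smaller than the noise. It is a systematic shift all the same, which follow-up-adjusted measures can address.

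Two other inferences fail. The Day 14 decision does not shorten AE observation, since 10.2 keeps the subject in follow-up whichever option is chosen; nor does it alone fix exposure, given the discretion after Day 28. And 80% closure does not mean that four in five subjects leave early: 18.4 refers to ulcers healed by Day 84, subjects with several wounds leave only when the last one heals, and a closure first seen at Visit 7 shortens nothing.

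**Conclusion.** The point holds as a conditional weakness in how safety is summarised. Length of AE observation is tied to the primary outcome, dressing duration is at unblinded discretion, and the supplied text contains no measure that accounts for either. There is no distortion if time to healing and continuation match between arms. Under the stated assumptions, a closure gap equal to the margin gives follow-up 13% to 25% longer in the slower arm and a spurious 3 to 5 points at 0.05 AEs per week; a 5-point closure gap under constant hazards gives about 2 points. Both the AE rate and the healing pattern are assumed.

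No primary or secondary efficacy conclusion is affected, and the documents do not show that a biased safety comparison will occur. The change is worth making because it costs little.

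**What to change.** In 4.2.4 and the SAP:

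1. Keep the crude percentages and label them descriptive.
2. Add AEs, device-related AEs and SAEs per subject-week of follow-up, with follow-up time summarised by arm.
3. Add incidence in a fixed Day 1 to Day 28 window, censored at exit, with number at risk.
4. Summarise days on the randomised dressing to Day 28 by arm. Because decisions are made per wound, state a subject-level definition, for example any study wound on the randomised dressing. Stop at Day 28: Visits 2 and 3 record the dressing name, whereas 10.4 does not clearly do so for Visits 4 to 7.

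Two sets of passages need reconciling first. Section 3.1 describes randomised dressing use for up to four weeks followed by standard of care, while 10.3 and the Table 9.3-1 footnote allow it to continue after Day 28; exposure cannot be defined until 3.1, 9.3, 10.2 and 10.3 agree. Section 10.3 also lists only device events and SAEs at Visit 3, while 11.2 requires all AEs, which bears directly on the Day 28 window.

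The cost is SAP wording and a few tables, with no extra visits or patients. AE and exit forms are already required; I assume that they carry onset and exit dates, as the protocol does not list their fields. The person-time figures rely on a roughly constant AE rate, which is why the fixed window should accompany them.

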5 POPULATION AND DURATION OF THE STUDY

It is proposed that the study is conducted in Poland, Germany, and Colombia. Additional sites in additional countries may be recruited. The study sample will be recruited from the Investigators available clinical population.

Individual subject duration of participation in the study is up to 12 weeks. It is anticipated enrolment will take 12 months and the overall study duration is anticipated to be approximately 18 months.

6 ENROLLMENT CRITERIA

6.1 Inclusion Criteria

Subjects must meet the following criteria:

TABLE: 6.1-1: Inclusion Criteria

Number	Inclusion Criteria
IC-1	Venous insufficiency as defined by CEAP Classification of C6
IC-2	At least one chronic venous ulcer (wound) amendable to treatment with AQUACEL® Ag+ Extra™ and Cutimed® Sorbact®
IC-3	Wound(s) that have been present for at least 60 days (2 months) and less than ≤18 months
IC-4	Reliable and available for follow-up, in the opinion of the investigator
IC-5	18 years or older at the time of consent
IC-6	Able and willing to provide informed consent
IC-7	Able to tolerate compression therapy for VLU (40 mmHg)
IC-8	Wound must be $\geq 1 \text{ cm}^2$ and $\leq 100 \text{ cm}^2$
IC-9	Must be able to be compliant with compression therapy
IC-10	ABPI should be in the range between 0.8 and 1.3

6.2 Exclusion Criteria

Subjects must be excluded from participating in this study if they meet any of the following criteria:

TABLE: 6.2-1: Exclusion Criteria

Number	Exclusion Criteria
EC-1	Known sensitivities or allergies to components of the AQUACEL® Ag+ Extra™ or Cutimed® Sorbact®
EC-2	Continued use of petroleum gel/ creams/ oil-based products on the target wound
EC-3	Active treatment for cancer or completed within the last 3 months
EC-4	Documented severe malnutrition at any time
EC-5	Malignant wounds or other than VLU wounds
EC-6	Systemic infection actively treated with antibiotics
EC-7	Patients with uncontrolled diabetes within last 3 months with HbA1c ≥ 10 . Subjects without diabetes do not require measurement of HbA1c if they have a glucose or HbA1c level measured over the past year.

Number	Exclusion Criteria
EC-8	Chronic conditions such as autoimmune disorders in an acute flare phase, which in the opinion of the investigator would directly impact wound healing. Use of immunosuppressant medications are allowed as long as they have been on a stable dose and regimen over the past three months

6.3 Relationship of Investigation Population to the Target Population

Silver and non-silver wound dressings are used to assist in the management of chronic wounds. The inclusion and exclusion criteria are representative of the population with chronic wounds who would be prescribed AQUACEL® Ag+ Extra™ and Cutimed® Sorbact® dressing.

7 INFORMED CONSENT PROCESS

Informed Consent must be obtained for all subjects prior to any study activities being performed or data collected. The Investigator or designee will review all relevant aspects of the study with the potential study subject that are relevant to the subject's decision to participate throughout the study. The investigator or designee will provide ample time for the subject to read and understand the IRB/EC approved Informed Consent Form and to consider participation in the study.

Informed consent will not be collected until all the patient questions have been answered to their satisfaction. If agreeable, the subject (or legally authorised representative) must sign and date the Informed Consent Form, along with the Investigator or designee. As required by country-specific regulatory agencies, a witness will sign the Informed Consent Form. The Subject must receive a copy of the signed Informed Consent, with the original remaining with the Investigator.

